11.4. Secondary Efficacy Analyses

1. The effect of treatment on the iGFR at the end of the 3-year treatment period (before the washout) will be evaluated using the same analytical approach employed for the primary outcome.
2. The effect of treatment on the eGFR at 4 months after randomization will be evaluated using the same analytical approach employed for the primary outcome.
3. The iGFR and eGFR time trajectories, estimated from periodical iGFR measures and quarterly serum creatinine and cystatin C measurements using the CKD-EPI SCr and the CKD-EPI SCr-SCysC equations^{34,35}, respectively, will be analyzed using linear mixed-effects models.⁴⁰⁻⁴² The main objective of the analysis will be to construct confidence interval for the effect of the intervention over three years of observation (treatment main effect) and investigate whether the effect of the intervention changes with time (time by treatment interaction).
4. Time to serum creatinine doubling or ESRD in the two treatment groups is subject to censoring due to dropouts or reaching the end of study before the participant experiences the event. Survival time will be defined as the time from randomization to the event (the first of serum creatinine doubling from baseline or occurrence of ESRD, defined as eGFR \leq 15 ml/min/1.73 m², hemodialysis, or kidney transplant) or, for participants who did not experienced an event, to the last study visit. Data will be summarized by means of Kaplan-Meier survival curves and by providing the proportions of participants surviving without events at 1, 2, 3 years, and at the end of the wash-out period along with their 95% CIs. Given the potentially small number of events, differences between study groups will be tested by means of the log rang test or by means of simple Cox regression models including a limited number of predictors in addition to treatment group.
5. The effect of treatment on the AER at the end of the wash-out period, based on the geometric mean of two AER measured at this time point and adjusted for the geometric mean of AER at baseline (Visit 3 and 4), will be investigated in a linear regression model framework as in the case of the primary outcome.

6. The effect of treatment on the AER at the end of the treatment period, based on the geometric mean of the AER measures at visit 15 and 16 adjusted for the geometric mean of AER at baseline (Visit 3 and 4) will be investigated as in #5.

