11.10. Sample Size

Since a variance-covariance matrix for the iGFR measures is not available and this matrix is essential in order to perform formal power calculations for a model with correlated errors, we performed alternative power calculations based on an intent-to-treat analysis within an ANCOVA framework. Specifically, we assumed that the primary hypothesis is tested in the following model:

$$M1: \text{iGFR at washout} = \text{iGFR at baseline} + \text{treatment group}$$

Compared to the model that will be used in the primary analysis, model M1 is simplified in two aspects. First, it does not use information from iGFR values measured at intermediate time points. Second, it does not include covariates such as the stratifying variables (HbA1c and UA) or other GFR predictors such as baseline AER. Both of these aspects may lead to loss of precision of the treatment effect estimate. Consequently, our sample size calculations should be considered as conservative.

The hypothesis being tested, i.e. the effect of treatment on iGFR at washout, corresponds to testing whether the treatment group factor in Model M1 is significant. The choice of the ANCOVA model for the purpose of power calculations is sensible, as residuals from a univariate model involving baseline iGFR as covariate fitted to data from RASS study conform to normal distribution. Sample size calculations were performed based on Cohen⁴⁵ and making the following assumptions:

1. Postulated effect on iGFR at washout (\cdot) = 3 ml/min/1.73 m². We deem this effect to be clinically meaningful and attainable. It is clinically meaningful because it would translate on average into a 10-year delay in the progression to ESRD. It is attainable because it is smaller than the difference in 3-year GFR that we observed in the JKS between subjects with serum UA \geq 4.5 mg/dl compared to those with levels below this value. The postulated effect was based on the following changes in GFR levels in the two treatment groups:

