 - a. Untreated group = 3 ml/min/1.73 m² per year. This estimate is based on data from the Joslin Kidney Study (JKS), in which the median GFR loss among 43 subjects meeting the above criteria was 3.1 ml/min/1.73 m² per year, with 70% of subjects having a GFR loss $>$ 1.5 ml/min/1.73 m² per year. Also, among 116 subjects from Steno who met the albuminuria and GFR criteria, but for whom serum uric acid values were not available, the median GFR loss was 3.3 ml/min/1.73 m² per year, with 71% of subjects having a GFR loss $>$ 1.5 ml/min/1.73 m² per year.
 - b. Treated group = 2 ml/min/1.73 m² per year. The average GFR loss in the JKS subjects with serum UA $<$ 4.5 mg/dl was 1.5 ml/min per year. On this basis, we conservatively assumed that the allopurinol treatment, if effective, would decrease the GFR loss to 2 ml/min per year (a 33% decrease compared to the untreated group).

2. Standard deviation (SD) of residual error = 10.1 ml/min/1.73 m². This was estimated based on the root-mean-squared error from a regression model with eGFR at 3 yrs as the dependent variable and baseline eGFR as the independent variable fitted to data concerning T1D patients from the Joslin Kidney Study meeting the PERL inclusion criteria.

Assuming a two-sided alpha error equal to 0.05, the effective sample size needed to detect the pre-specified treatment effect ($\delta = 3$ ml/min/1.73 m²) at washout adjusted for baseline iGFR with 80% power is equal to n=180 per group. To take into account the anticipated overall dropout rate (up to 5%/yr or 15% over the entire duration of the study) and drug discontinuation or non-compliance in the treatment group (up to 2%/yr or 6% over the entire duration of the study), and to maintain the desired

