5.2.2. Estimand for iGFR time trajectory estimated from repeated iGFR measurements

This is de-facto (effectiveness) estimand for repeated iGFR measures with the following attributes:

A1. Target population: Individuals with T1D meeting the inclusion/exclusion criteria specified in the Study Protocol.

A2. Variables of interest: Repeated measures of iGFR at Visits 11, 16, 17.

A3. Strategies for different groups of IC events: The same as those used for primary estimand (see Section 5.1)

A4. Population summary to compare treatments: Population-average treatment effect on the slope of iGFR trajectory

5.2.3. Estimand for estimated Glomerular Filtration Rate (eGFR) at 4 months after randomization (Visit 7)

This is de-facto (effectiveness) estimand for eGFR at 4 months after randomization with the following attributes:

A1. Target population: Individuals with T1D meeting the inclusion/exclusion criteria specified in the Study Protocol.

A2. Variable of interest (endpoint): eGFR at 4 months after randomization as estimated from serum creatinine and cystatin C using the CKD-EPI SCr and the CKD-EPI SCr-SCysC equations (Inker et al, 2012, Fan et al, 2015). This endpoint is employed to measure a transient, hemodynamic effect that the study medication may have on GFR.

A3. Strategies for different groups of IC events: The same as those used for primary estimand (see Section 5.1)

A4. Population summary to compare treatments: Population-average treatment effect on eGFR at 4 months after randomization.

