No formal interim analyses of the primary endpoint will be conducted, therefore the nominal α level to be used at the final analysis will be 0.05 for the primary endpoint. All other secondary outcomes will also be tested at the 0.05 level, with no adjustment for multiplicity. Many of the models used in the analyses include baseline covariates, such as stratifying variables (serum uric acid (sUA), HbA1C, clinical site), iGFR, albuminuria status (subjects who qualified by ACR or AER or were albuminuric at baseline vs. subjects who qualified by eGFR slope and were normoalbuminuric at baseline), AER, and time, and time by treatment interaction. If there are problems with fitting these models, due, for example, to lack of convergence to optimal values, covariates will be eliminated from the models in the following order: baseline AER, albuminuria status, serum uric acid (sUA), HbA1c, and clinical site. More detailed information about these covariates is included in Section 6.4.

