6.7. Analyses for secondary estimands

In this section we present analyses aligned with secondary estimands defined in section 5.2. Analyses will be performed using the multiple imputation technique, except those involving time-to event endpoints (sections 6.7.5, 6.7.8).

6.7.1. iGFR at the end of the 3-year treatment period (Visit 16, before the washout)

In this section we describe the analysis (estimator) aligned with the estimand for iGFR at the end of the 3-year treatment period (Visit 16, before the washout) endpoint defined in Section 5.2.1.

The least square means at Visit 16, estimate of treatment effect *at Visit 16* adjusted for baseline covariates, their 95% confidence interval and P-value will be obtained as part of the primary analysis of the primary estimand (Equation (6.1) in section 6.1.1). In the context of this secondary endpoint, we are interested in the fixed effect β_{12} , which represents the treatment effect at Visit 16 adjusted for stratifying variables and baseline covariates. To assess the hemodynamic/transient effect of the allopurinol, we will estimate the contrast $\beta_{12} - \beta_{13}$ between the treatment effect at Visit 16 (before washout) compared to that at Visit 17 (after washout).

6.7.2. iGFR time trajectory estimated from repeated iGFR measurements

This analysis is aligned with the estimand defined in Section 5.2.2

Estimand	See section. 5.2.2 for definition
Analysis	Analysis of the Secondary Endpoint: iGFR time trajectory estimated from repeated iGFR measurements.
Analysis Set	ITT Population
Methods	Linear mixed-effects model for longitudinal iGFR measures using multiple imputation technique.
Dependent Variable	iGFR measured at Visits V11 (80 weeks) , V16 (156 weeks) and V17 (164 weeks after randomization)
Model	
Fixed effects associated with:
 
 • Stratifying variables: sUA, HbA1c, study center • Treatment group • Time since randomization (in years) associated visit windows defined in section 6.3 • Time by treatment group interaction • Albuminuria status with 2 levels • Baseline AER geometric mean (at Visits 3 and 4 combined) expressed on log to base 10 scale • Baseline iGFR 
Subject-specific random effects
 
 • Random intercept for iGFR • Random slope for iGFR

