Results	
 • iGFR slope estimates and 95%CIs by treatment group • Estimate of a treatment effect measured as a difference between average slopes of iGFR versus time for allopurinol and placebo groups adjusted

	for stratifying variables and baseline covariates 
 • 95% confidence interval for treatment effect • P-value for treatment effect
--	--

6.7.3. eGFR at 4 months after randomization (Visit 7)

Estimand	See section 5.2.3 for definition
Analysis	Analysis of the Secondary Endpoint: eGFR at 4 months after randomization (Visit 7).
Analysis Set	ITT Population
Methods	Linear model using multiple imputation technique.
Dependent Variable	eGFR measured at Visit V7 (16 weeks after randomization)
Model	Fixed effects associated with: 
 • Stratifying variables: sUA, HbA1c, study center • Treatment group • Albuminuria status with 2 levels • Baseline AER geometric mean (at Visits 3 and 4 combined) expressed on log to base 10 scale • Baseline eGFR
Results	
 • Least square eGFR means at Visit 7 by treatment group. • Estimate of treatment effect at Visit 7 adjusted for stratifying variables and baseline covariates • 95% confidence interval for treatment effect • P-value for treatment effect

6.7.4. eGFR time trajectory

Estimand	See section 5.2.4 for definition
Analysis	Analysis of the Secondary Endpoint: eGFR time trajectory estimated from repeated eGFR measurements using multiple imputation technique..
Analysis Set	ITT Population
Methods	Linear mixed-effects model for longitudinal eGFR measures using multiple imputation technique.
Dependent Variable	Post-randomization eGFR measured from Visits V6 through V17
Model	Fixed effects associated with: 
 • Stratifying variables: sUA, HbA1c, study center • Treatment group • Time since randomization in (in years) associated visit windows defined in section 6.3 • Time by treatment group interaction • Albuminuria status with 2 levels • Baseline AER geometric mean (at Visits 3 and 4 combined) expressed on log to base 10 scale • Baseline eGFR Subject-specific random effects 
 • Random intercept for eGFR • Random slope for eGFR

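### The iGFR trajectory test (SAP 5.2.2, 6.7.2) asks whether the arms diverge after week 80, not whether treatment changed iGFR over three years as Protocol 11.4 item 3 intends

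*SAP*

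**What the plan says.** SAP 5.2.2 defines the variable as "Repeated measures of iGFR at Visits 11, 16, 17" and the summary measure as the treatment effect on the slope. SAP 6.7.2 fits a linear mixed model to those three visits; its row for the dependent variable begins "iGFR measured at Visits V11 (80 weeks" and goes on to Visits 16 and 17, with no baseline visit. Its fixed effects include treatment group, time since randomisation, time by treatment, and baseline iGFR as a covariate that is constant over time; intercept and slope are random. The treatment effect reported, with its interval and p-value, is the "difference between average slopes of iGFR versus time for allopurinol and placebo groups". SAP section 6 sets the level: "All other secondary outcomes will also be tested at the 0.05 level, with no adjustment for multiplicity".

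Protocol 11.4 item 3 gives the main objective for the trajectories as to "construct confidence interval for the effect of the intervention over three years of observation", which it identifies with the treatment main effect. Whether the effect changes with time (the interaction) is a further question. SAP section 3 lists the departures from the protocol. Its item 3.2 takes baseline iGFR out of the response for the primary model, but no item says that the trajectory question now starts at week 80.

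**The concern.** With a free treatment main effect, the slope difference is identified only by what happens between the first and last response visits. Baseline iGFR as a constant covariate shifts each person's level and adds nothing to the slope. The null hypothesis is therefore no further divergence after week 80. A reader of the results would take it to be no effect on iGFR decline since randomisation.

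This matters in two ways. First, about half of the effect that the trial was sized for falls outside the contrast, and the slope rests on a short span of time. Second, an early benefit that is maintained would give a slope difference near zero beside a positive primary result. Someone could read that pair as evidence against an effect on decline.

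**Working it through.** **Inputs from the documents.** Protocol 11.10: two-sided 0.05; effect 3 ml/min/1.73 m² at washout; losses of 3 and 2 per year, hence a slope difference of 1 per year; residual SD 10.1 given baseline; dropout 15%. SAP section 1: 530 participants, so 265 per arm and 265 × 0.85 = 225 analysed. Visit times: scheduled weeks 80, 156 and 164; SAP Table 6.3.2 assigns 80, 164 and 174.

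**Assumptions.** Protocol 11.10 says that the iGFR covariance matrix is unavailable. I took measurement-error SD 2 to 6, true baseline SD 16 and no correlation between level and slope. The slope SD is set so that the SD of Visit 17 given baseline is 10.1. A year is 52.18 weeks.

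**1. The plan's own figure.** n = 2(1.960 + 0.842)² × 10.1² / 3² = 178 per group. The protocol's effective sample size "at washout adjusted for baseline iGFR with 80% power is equal to n=180 per group", so this agrees. The Model M1 column of Table 1 also reproduces: .874, .863, .851, .831, .818, .805.

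**2. What the contrast sees.** Let d(t) be the difference between arms. The slope difference is Σ(t − t̄)d(t) / Sxx over the response visits, where Sxx = Σ(t − t̄)².
- Constant effect of 1 per year: the share of the week-164 benefit accrued by week 80 is 80/164 = 49%.
- Benefit of 3 by week 80, then held: d = 3, 3, 3, so the slope difference is 0. The test rejects 5% of the time, 2.5% in the direction of benefit.

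**3. Precision.** Scheduled times in years are 1.533, 2.990 and 3.143, with mean 2.555, so Sxx = 1.045 + 0.189 + 0.345 = 1.58. With Visit 4 at time 0 the mean is 1.917 and Sxx = 3.673 + 0.147 + 1.152 + 1.504 = 6.48. At the SAP's assigned times the three-visit Sxx is 1.96.

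**4. Power for 1 per year, 225 per arm.** Present model: per-person variance = slope SD² + error SD²/Sxx. At error SD 4 and scheduled times the slope SD is 2.68, so the variance is 7.18 + 10.13 = 17.3. Then SE = √(2 × 17.3/225) = 0.392, and power = Φ(1/0.392 − 1.96) = 72%. With Visit 4 as a response and a common baseline mean, the variance is 1/(t′V⁻¹t), where t holds the three follow-up times and V is the covariance of those visits given Visit 4. This gives SE 0.292 and power 93%.

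| Error SD | Present, 80/156/164 | With Visit 4 | Loss | Present, 80/164/174 | With Visit 4 | Loss |
|---|---|---|---|---|---|---|
| 2 | 86% | 92% | 5 | 91% | 94% | 4 |
| 3 | 80% | 92% | 12 | 86% | 95% | 9 |
| 4 | 72% | 93% | 21 | 79% | 95% | 16 |
| 6 | 54% | 95% | 41 | 63% | 97% | 34 |

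Losses are in percentage points, from unrounded values. The right-hand columns assume that visits fall at the assigned times.

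**5. Robustness.** I repeated this with 204 per arm (240 × 0.85), the effect cut by 6% for non-compliance, baseline SD 12 to 20 and level–slope correlation −0.3 to 0.3. The losses are 5 to 10 points at error SD 2, 12 to 18 at SD 3, 20 to 27 at SD 4 and 39 to 46 at SD 6.

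**6. Transient on-drug effect h** (present at Visits 11 and 16, gone at Visit 17; scheduled times). Present model: −0.588h/1.58 = −0.37h per year. With Visit 4 added: (−0.384 + 1.074)h/6.48 = +0.11h per year.

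**The case against.** The trial is not blind to early benefit, although a reader might infer that. Equation 6.1 in SAP 6.6.1 gives treatment effects at Visits 11, 16 and 17. The primary test uses the last, SAP 6.7.1 uses Visit 16, and the eGFR trajectory starts at Visit 6. An early, sustained benefit would appear as three similar visit effects beside a flat later slope, which is coherent. This stands, and it confines the problem to one secondary test.

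A reader might also infer a loss of 20 points or more outright. The documents do not support that, because they give no iGFR error SD. With 6% non-compliance, 20 points is reached only at an error SD of about 3.6 to 4.2 or more. The documents claim no power for this test.

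The protocol ties its three-year effect to the treatment main effect, which the SAP model contains, so reporting that term or a joint test would be a smaller repair. This stands in part. A joint test would detect either pattern but gives no single slope estimate. The main effect alone, with time counted from randomisation, is a difference extrapolated back to week 0; under the protocol's linear effect its expected value is zero.

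A post-randomisation slope might be a deliberate way to avoid acute haemodynamic effects. SAP 5.2.2 and 6.7.2 do not say so, and mixing on-drug Visits 11 and 16 with off-drug Visit 17 makes the present slope the more sensitive one (−0.37h against +0.11h).

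Last, if the effect plateaus, the four-visit linear model is misspecified. Effects of 0, 3, 3, 3 give a slope difference of 3 × 1.917/6.48, about 0.9 per year, although the arms are parallel after week 80. This stands and should be stated with the result.

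**Conclusion.** The point holds for this secondary analysis. That the p-value concerns divergence after week 80 follows from the model as written, with no variance assumption. So does the zero expected slope difference for a benefit complete by week 80 and held. The 49% needs only the protocol's constant-rate effect. The mismatch with Protocol 11.4 item 3 is not declared in SAP section 3.

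The power loss is conditional. At 225 per arm and a difference of 1 per year it runs from 4 to 5 points at error SD 2 to 34 to 41 at SD 6, on the assumptions listed. Power was lower at every value tried, but no single figure can be attached to the plan. The primary analysis and its power are unaffected.

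**What to change.** In SAP 5.2.2 and 6.7.2:
- Make iGFR at Visits 4, 11, 16 and 17 the response, with Visit 4 at time 0.
- Drop baseline iGFR as a covariate and the treatment main effect, so that the arms share a mean at randomisation.
- Keep time, time by treatment, the other covariates and the random intercept and slope. Report time by treatment as the effect on the slope since randomisation.
- If the three-visit slope is also kept, label it as the slope from week 80 onward.
- List the change in SAP section 3.

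The cost is wording and one model statement. SAP 6.4 counts one missing baseline iGFR, and Protocol 11.3 already used that visit as a response. Two downsides should be stated: a transient on-drug effect h enters the new slope at about +0.11h per year, and an effect that plateaus is summarised as an average linear slope.

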6.7.5. Time to serum creatinine doubling or ESRD

Estimand	See section 5.2.5 for definition
Analysis Set	ITT Population
Methods	Proportional hazards model for interval censored data.
Dependent Variable	Time to composite endpoint of serum creatinine doubling or ESRD
Proportional Hazards Model	Fixed effects associated with: 
 • Stratifying variables: sUA, HbA1c, study center • Treatment group • Albuminuria status with 2 levels • Baseline AER geometric mean (at Visits 3 and 4 combined) expressed on log to base 10 scale • Baseline iGFR
Results	
 • N(%) of subjects with doubled serum creatinine or ESRD during the course of the study • Hazard ratio of allopurinol to placebo • 95% confidence interval for hazard ratio • P-value for treatment effect

6.7.6. Urinary AER at the end of the wash-out period

Estimand	See section 5.2.6 for definition
Analysis Set	ITT Population
Methods	Linear model using multiple imputation technique.
Dependent Variable	Two AER measures obtained at Visit 17 and summarized using the geometric mean expressed on logarithm base to 10 scale
Model	Fixed effects associated with: 
 • Stratifying variables: sUA, HbA1c, study center • Treatment group • Albuminuria status with 2 levels • Baseline AER geometric mean (at Visits 3 and 4 combined) expressed on log base to 10 scale • Baseline iGFR
Results	
 • Predicted urinary AERs at Visit 17 by treatment group obtained by antilog transformation applied to corresponding least square means • Estimate of treatment effect at Visit 17 expressed on percent change scale using antilog transformation. • 95% confidence interval for treatment effect expressed on percent change scale using antilog transformation. • P-value for treatment effect

6.7.7. Urinary AER during the last three months of the treatment period (Visits 15 and 16)

Estimand	See Section 5.2.7 for definition
Analysis Set	ITT Population
Methods	Linear model using multiple imputation technique.
Dependent Variable	Two AER measures obtained at Visit 15 and 16 are summarized using the geometric mean expressed on logarithmic scale
Model	Fixed effects associated with: 
 • Stratifying variables: sUA, HbA1c, study center • Treatment group • Albuminuria status with 2 levels • Baseline AER geometric mean (at Visits 3 and 4 combined) expressed on log base to 10 scale • Baseline iGFR
Results	
 • Predicted AERs at the end of treatment period by treatment group obtained by antilog transformation applied to corresponding least square means. • Estimate of treatment effect at the end of treatment period adjusted for baseline covariates expressed on percent change scale using antilog transformation. • 95% confidence interval for treatment effect expressed on percent change using antilog transformation. • P-value for treatment effect

